2.5.2 Known Potential Benefits

There is no direct benefit to the study participant. There is the potential benefit of advancing

scientific understanding of influenza transmission from participation in this study.

3 IDENTIFICATION OF INDEX CASES FOR CHIVITT (DONORS PROTOCOL)

3.1 Donor Protocol – Design

We will enroll persons aged 18 through 59 years of age into this EMIT-2 Donor Protocol. Generally healthy subjects without known risk factors for severe influenza complications who have acute symptomatic influenza infection will be eligible for enrollment. The screening process will include a clinical evaluation for general health status, assessment of drug and alcohol dependence and abuse, and assessment of smoking/vaping history.

Recruitment

We learned from focus groups that many potential donors do not generally go to a clinic when they are sick and may not ever have the cause of their influenza-like-illness (ILI) diagnosed. We also learned that obtaining and paying for a flu test for purposes of determining eligibility for the CHIVITT is a time and cost barrier to participation as a donor. Therefore, to detect cases early enough in the incubation period, we are adding several new options for flu testing to the original strategy of recruiting donors during clinic visits.

Therefor we will take multiple approaches to Donor recruitment.

Clinics and Urgent Care Centers - Donor recruitment will involve identifying influenza case patients at local urgent care centers, emergency rooms, campus health centers, and at local provider offices. Initial recruitment will be focused on the preliminary identification of potential participants being seen within the UMMC Emergency Department (Baltimore, MD), the UM Maryland Immediate Care (UMIC, Baltimore, MD), UM Urgent Care - Downtown; UM Urgent Care - Columbia; University of Maryland Faculty Physicians, Inc. at Waterloo Crossing, the University of Maryland Health Center (UHC, [name]), Express Healthcare, LLC ([name]), and Johns Hopkins Medical Institutions (JHMI). However, with ongoing collaborations within the medical community, there will be an expansion of potential urgent care centers, medical practices, and other partners which might provide referrals of influenza patients as donors.

Pop-Up Kiosks. CLIA-waived rapid flu tests will be administered at “pop-up kiosks” on campuses or other locations thought to have a high likelihood of yielding individuals with positive flu tests. Kiosks will be staffed by trained study personnel. Visitors to the kiosk who want to be tested will self-swab, provide their email address, and answer questions about fever, cough, and sore throat. Trained study personnel will perform the rapid flu test and link the test to the visitor’s email address. Study recruitment fliers will be distributed. Individuals who get tested will receive an information sheet describing the risks and benefits of the rapid test, along with study materials. These settings where healthy students, families and/or other adults congregate (such as dormitories, student lounges, barber shops) will allow investigators to raise awareness of the study, provide the means for no-cost tests and improve the chances of enrolling individuals with the influenza very early in the course of their disease.

Lord Baltimore Hotel – We will provide CLIA-waived flu testing kiosk at the Lord Baltimore Hotel during the quarantine CHIVITT to facilitate identifying eligible donor volunteers. These individuals will have heard about the study via social media, fliers, or word of mouth, and have ILI but not been tested.

In these situations, they can obtain a flu test at the Lord Baltimore Hotel during periods when we are recruiting Donors.

Recipient Registry - individuals who are enrolled in the EMIT-2 Recipient Registry (HP-00097730), may be provided FDA approved home influenza rapid test kits during their screening or follow-up clinic visits if test kits are available. (This will be described in the Recipient Registry Protocol.) If they contract influenza-like illness during a CHIVITT donor recruitment, they can test themselves and volunteer as a donor if they are available and otherwise eligible.

For all potential Donors, a review of available electronic medical records may be necessary to assess for the presence of exclusion criteria prior to formal signed informed consent—this would require IRB approval to waive the HIPAA authorization to obtain identifiable private information for this pre-screening process, as it would not be practicable to conduct this research without the waiver.

Potential participant donors who have been identified at external care centers, kiosks, campus/community outreach services, or through self-testing (registry participants only) and have passed a phone screening, may verbally consent to be screened and transported to the research facility.

3.2 Donor – Eligibility Criteria

Inclusion Criteria

1. Provides written informed consent, able to comply with the planned study procedures, available for between 2 and 5 days stay in the research quarantine unit for the CHIVITT, and have the ability to attend the scheduled follow-up visits.
2. Subjects must be able to comprehend the study requirements, as evidenced by a score of $\geq 70\%$ or better on the comprehension assessment (two attempts permitted).
3. Males and non-pregnant, non-breastfeeding females¹ aged ≥ 18 and ≤ 59 years of age, at time of initial consent.

¹*Pregnancy and breastfeeding status to be determined by self-report*

4. Laboratory-confirmed influenza infection² within the past 48 hours at time of entry into the exposure event.

²*A rapid antigen test in the setting of known local influenza activity and with symptoms suggestive of influenza at that time is acceptable.*

5. Within the past 48 hours at time of entry into the exposure event, onset of influenza-like illness, as defined as fever (measured oral temperature of $\geq 100.2^{\circ}\text{F}$ or self-reported fever in the absence of a measured temperature) AND cough or sore throat, or onset of less specific symptoms with a positive molecular test for influenza virus infection.
6. No self-reported or known history of alcohol or drug abuse within the past two years and no illicit drug use within the last 30 days.
7. Do not have clinically significant medical, psychiatric, and chronic or intermittent health conditions including those listed in Exclusion Criteria.

8. Does not have an ongoing symptomatic condition³ for which subject has had or has ongoing medical investigations but has not yet received a diagnosis or treatment plan.
³e.g., *ongoing and debilitating fatigue without a diagnosis for the symptom.*
9. Agrees to the collection of specimens for secondary research.

Exclusion Criteria

1. Female of childbearing potential who is breastfeeding or has positive urine pregnancy test upon admission to the hotel quarantine unit.
2. Presence of self-reported or medically documented significant medical or psychiatric condition(s)⁵
⁵*Significant medical or psychiatric conditions include but are not limited to:*
 - a. *Respiratory disease (e.g., chronic obstructive pulmonary disease [COPD], asthma, cystic fibrosis) requiring daily medications⁶ currently or any treatment of respiratory disease exacerbations or hospitalizations for acute respiratory illnesses (e.g., asthma exacerbation) in the last 5 years.*
⁶*Asthma medications: inhaled, oral, or intravenous (IV) corticosteroids, leukotriene modifiers, long and short acting beta agonists, theophylline, ipratropium, biologics.*
 - b. *Significant cardiovascular disease (e.g., congestive heart failure, cardiomyopathy, ischemic heart disease) or history of myocarditis or pericarditis as an adult.*
 - c. *Neurological or neurodevelopmental conditions (e.g., epilepsy, stroke, seizures, encephalopathy, focal neurologic deficits, Guillain-Barré syndrome, encephalomyelitis or transverse myelitis).*
 - d. *Ongoing malignancy or recent diagnosis of malignancy, including leukemia; treated, non-melanoma skin cancers are permissible.*
 - e. *An autoimmune disease.*
 - f. *An immunodeficiency of any cause.*
 - g. *A blood disorder (e.g., sickle cell disease)*
 - h. *Endocrine disorders (e.g., diabetes)*
 - i. *Liver, kidney, metabolic disorders*
 - j. *BMI ≥40 kg/m²*
 - k. *Any other condition or behavior that in the opinion of the PI would affect the ability to participate in the transmission study over the next several days.*
3. Presence of immunosuppression or any medications that may be associated with impaired immune responsiveness⁷.
⁷*Including, but not limited to, corticosteroids exceeding 10 mg/day of prednisone equivalent, immunoglobulin, interferon, immunomodulators, cytotoxic drugs, or systemic corticosteroids or other similar or toxic drugs during the preceding 2-month period. Low dose topical and intranasal steroid preparations used for a discrete period are permitted.*
4. Is a habitual smoker⁸ of tobacco, marijuana, or e-cigarettes per self-report.

⁸*Habitual smokers are those who smoke or vape more than four cigarettes, other tobacco products, e-cigarettes or marijuana in a week for more than three months or use an inhaled nicotine or marijuana product more than 3 days a week on average. Edible or patch forms of tobacco or marijuana products do not constitute an exclusion.*

5. Known allergy or intolerance to treatments for influenza and other respiratory infections (including but not limited to acetaminophen/paracetamol).
6. History of a previous severe allergic reaction to medicines of any kind with generalized urticaria, angioedema, or anaphylaxis.
7. Presence of co-infection with SARS-CoV-2, as detected via a multiplex nucleic acid amplification test (e.g., Biofire).
8. Participating in any other interventional clinical research study that has a scheduled intervention 30 days prior to the CHIVITT or 30 after discharge from the research quarantine unit.
9. Any condition, to include medical and psychiatric conditions, that in the opinion of the Investigator, might interfere with the safety of the subject or the study objectives.

4 ENROLLMENT OF RECIPIENTS FOR CHIVITT

From among the pool of already screened subjects under the EMIT-2 Recipient Protocol (UMB IRB HP-97730), we will contact these potential volunteers for agreement to consent to participate in a CHIVITT. These subjects will have recent (within the past year) serological assessment of anti-influenza antibody which may predict whether they may be vulnerable to an influenza strain (matching that of the Donor virus strain); this will be done from serum specimens collected under the EMIT-2 Recipient Protocol.

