4.1 Recipient Eligibility Criteria

Inclusion Criteria

1. Enrolled in the Recipient Protocol (UMB IRB HP-97730)
2. Provides written informed consent, able to comply with the planned study procedures, be available for an up to ~14-day stay for the CHIVITT and have the ability to attend the scheduled follow-up visits.
3. Subjects must be able to comprehend the study requirements, as evidenced by a score of $\geq 70\%$ or better on the comprehension assessment (two attempts permitted).
4. No significant change (for the worse) in general health history or in concomitant medication use, as compared from their responses collected during screening (EMIT-2 Recipient Protocol).
5. Agree not to meet with other participants (recipients or donors) outside of the programmed exposure events during the course of their participation in the CHIVITT.

Exclusion Criteria

1. Female of childbearing potential who has a positive urine pregnancy test within 24 hours of admission to the hotel quarantine unit or is breastfeeding or planning to become pregnant within 2 months after entry into a CHIVITT.
2. Presence of infection with influenza, SARS-CoV-2, or other respiratory pathogens detected via a multiplex nucleic acid amplification test (e.g., Biofire) at admission to the hotel quarantine facility.
3. Within the past 72 hours, presence of influenza-like illness, as defined as fever of $\geq 100.2^{\circ}\text{F}$ AND cough or sore throat, in the absence of an alternative cause.
4. Receipt of any blood products within the past 2 months.
5. Does not agree to provide permission for secondary research use of extra samples collected and stored specimens.
6. Habitual smoker of tobacco, marijuana, or e-cigarettes per self-report. (*Habitual smokers are those who smoke or vape more than four cigarettes, other tobacco products, e-cigarettes or marijuana in a week for more than three months or use an inhaled nicotine or marijuana product more than 3 days a week on average. Edible or patch forms of tobacco or marijuana products do not constitute an exclusion.*)
7. Self-reported or known history of alcohol or drug abuse in the past two years and/or illicit drug use within the last 30 days. (*Prescribed stimulants for the treatment of ADHD and cannabinoids use do not constitute exclusionary criteria*)
8. Has an ongoing symptomatic condition¹ for which the subject has had or has ongoing medical investigations but has not yet received a diagnosis or treatment plan.

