6 CHIVITT STUDY DESIGN

Each CHIVITT is planned to be conducted with discrete cohorts of Recipients and Donors. The size of each cohort and numbers of Recipients and Donors will vary from cohort to cohort, but the general size of a cohort may consist of up to 20 Recipients and up to 5 Donors per CHIVITT, which would span an approximate 2-week period. The number of Recipients will be determined by each individual's availability and whether their most recent serum antibodies have demonstrated a relative low titer against the influenza virus to be transmitted in the CHIVITT. To maintain the size of the recipient group, we may consider bringing in new recipients during the quarantine study if a significant number of original recipients are infected on the same day. The number of Donors will be determined by the number of participants which are identified with acute symptomatic influenza infection during the time of a CHIVITT cohort's stay.

The CHIVITT studies are anticipated to occur during the peak of local seasonal influenza transmission (e.g., January and February). Timing of the study will be constrained by the necessity to rent the facility for prespecified calendar dates. It is intended that the local seasonal influenza activity will be closely monitored, including the virus subtypes which are predominantly circulating. During the peak of the local seasonal influenza activity, a cohort of Recipients will be contacted to request their willingness to reside up to ~2 weeks on the quarantine research unit for a CHIVITT. The selection of Recipients from the pool of potential Recipients will be partially determined by the demonstration of low antibody titers against the circulating influenza virus, which has been measured in the past year (under the EMIT-2 Recipient Protocol, UMB IRB HP-97730). Potential Recipients will be given some time (\leq one week) to decide whether to participate and they must complete an IRB-approved consent form for the CHIVITT study.

Meanwhile, during the peak of community-wide local seasonal influenza the study team will be attempting to rapidly identify healthy adults with acute and symptomatic influenza infection for consent to participate as Donors in the CHIVITT cohort. It is intended that there could be multiple Donors identified during a ~2-week period; each of these Donor individuals could be introduced into the CHIVITT cohort in an overlapping or sequential fashion, to provide more opportunities for transmission events.

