The success of each CHIVITT cohort will be influenced by the unpredictability of an influenza season, which influenza viruses may be circulating, willingness or availability of Recipients for each cohort, and the ability to identify and consent Donors for each cohort. To mitigate these factors, we will enroll sufficient potential

recipients that only a fraction are needed in any one season, multiple cohorts will be studied each year, and multiple clinical sources will participate in recruiting donors.

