8 CHIVITT STUDY PROCEDURES/EVALUATIONS

8.1 Study Procedures

8.1.1 Admission/entry to a CHIVITT cohort

- Obtaining of informed consent or confirmation of signed informed consent
- Vital signs (including SpO₂, HR, RR, BP, and oral temperature) and height and weight will be obtained
- A targeted physical examination may be performed, as directed by the medical history, medications, and vital signs assessment. An absence of significant past medical history, concomitant prescription medications, and abnormalities in vital signs will not require a physical examination.
- Review and record medical history* and concomitant medications†.
 - *All significant past and current diagnoses will be documented. All signs and symptoms (regardless of severity) that the subject has experienced within 30 days prior to screening will be documented. Medication allergies will also be documented on this form.
 - †All prescription and non-prescription medications, alternative therapies, and vaccines taken within 90 days prior to screening or since the last study visit should be documented.
- For Donors and Recipients, performance of a multiplex influenza, SARS-CoV-2, respiratory virus panel test (e.g., BioFire Respiratory Virus panel)
- For Donors, collection of a respiratory sample for viral quantitation
- Venous whole blood (~10 mL) collection for HAI and FRNT assays and the storage of remaining volumes for secondary research
- For Recipients only, Nasal wash specimen (~5-10 mL) will be collected.
- Additional nasal swab and a saliva sample for research tests (Participants will be asked to collect a saliva sample using a standard protocol and by spitting into a screw cap specimen cup or 50 mL polypropylene screw cap tube).
- For Donors, Exhaled breath sampling within 24 hours of entry.
- Point of care urine pregnancy test for donor and recipient females of childbearing potential within 24 hours of admission to the hotel quarantine unit (to be completed prior to any exposure events)

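### Recipients are selected partly on serum up to a year old, and Section 4.1 does not address influenza vaccination or recovered influenza since that sample

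*Protocol*

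**What the plan says.** Section 4 draws Recipients from people already screened under the separate Recipient Protocol: "These subjects will have recent (within the past year) serological assessment of anti-influenza antibody". Section 6 says that selection is "partially determined by the demonstration of low antibody titers against the circulating influenza virus, which has been measured in the past year". It gives January and February as the example of when cohorts run.

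The nearest criteria in Section 4.1 concern current illness. Exclusion 2 is "Presence of infection with influenza, SARS-CoV-2, or other respiratory pathogens detected via a multiplex nucleic acid amplification test" at admission. Exclusion 3 begins "Within the past 72 hours, presence of influenza-like illness". Inclusion 4 asks only whether general health or medication has changed for the worse since screening. No criterion names influenza vaccination, or influenza that has resolved, since the qualifying serum.

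Section 8.1.1 collects two relevant items at admission. Blood is drawn for HAI and FRNT, and "vaccines taken within 90 days prior to screening or since the last study visit should be documented". Neither is tied to eligibility or selection. Section 9.1.3 counts an HAI titer of 40 or more at one month as seropositive with no condition on the starting titer, and it does not say which sample is the baseline for seroconversion.

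**The concern.** A serum drawn up to a year before a January or February cohort can predate the autumn vaccination period and the first weeks of the current season. A person vaccinated or infected in between may still be selected on a titer that no longer describes them.

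Two things could follow. If such people resist infection and are counted as non-cases, they lower the attack rate on which the power statement in Section 9.2 depends. If their raised titer at one month meets the seropositive definition, they are counted as secondary cases in both arms, which blurs the contrast. Section 2.3 makes the program's aims contingent on producing secondary infections, so the attack rate deserves protection.

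**Working it through.** **Inputs from Section 9.2.** Control SAR 25%; one-sided alternative; alpha 5%. Air hygiene: 79% reduction, 54 in an intervention group, power 84%. Hand hygiene and face shield: 76% reduction, 63 in an intervention group, power 84%. The control group size is not given, so equal groups are assumed.

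**Formula.** With n per group and p̄ = (p1 + p2)/2:
- se0 = √[2·p̄(1−p̄)/n]
- se1 = √[(p1(1−p1) + p2(1−p2))/n]
- power = Φ[(|p1−p2| − c − 1.645·se0)/se1], where c = 1/n with continuity correction and 0 without.

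**Reproducing the plan's figure, n = 54.** p1 = 0.25 and p2 = 0.25 × 0.21 = 0.0525, so p̄ = 0.15125, se0 = 0.0690 and se1 = 0.0663.
- Corrected: (0.1975 − 0.0185 − 1.645 × 0.0690)/0.0663 = 0.99, giving 83.9%. This matches the stated 84%.
- Uncorrected: (0.1975 − 1.645 × 0.0690)/0.0663 = 1.27, giving 89.8%.

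**n = 63.** p2 = 0.25 × 0.24 = 0.06. Corrected power is 86.3% and uncorrected 91.1%, so the corrected formula misses the stated 84% by about 2 points. A two-sided uncorrected test gives 82.7% (n = 54) and 84.7% (n = 63), close to both stated figures. The Protocol does not say which formula was used, so the change in power matters more here than its level.

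**Route 1: newly immune Recipients are non-cases.** Let v be the share who became immune after the qualifying serum. The Protocol gives no value, so 10% to 40% is an assumption. Then p1 = 0.25(1 − v), with the same relative reduction.

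| v | Control SAR | n=54 corrected | n=54 uncorrected | n=63 corrected | n=63 uncorrected |
|---|---|---|---|---|---|
| 0 | 25% | 83.9% | 89.8% | 86.3% | 91.1% |
| 10% | 22.5% | 78.7% | 86.1% | 81.5% | 87.7% |
| 20% | 20% | 72.4% | 81.6% | 75.6% | 83.4% |
| 30% | 17.5% | 65.1% | 76.1% | 68.4% | 78.0% |
| 40% | 15% | 56.6% | 69.5% | 60.1% | 71.5% |

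**Route 2: newly immune Recipients are all counted as cases through HAI of 40 or more.** Then v is added to both arms. At v = 10%, n = 54: p1 = 0.225 + 0.10 = 0.325 and p2 = 0.04725 + 0.10 = 0.147. Corrected power is 62.2% and uncorrected 70.6%. For n = 63 (0.325 against 0.154), corrected power is 65.7%. This is the extreme of the route, since not every such person need reach the threshold.

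The two routes move the observed SAR in opposite directions, but both lower power.

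**The case against.** Several stronger readings are tempting, and the Protocol does not support them.

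- *That no rule exists anywhere.* Absence can be asserted only for Section 4.1. The Recipient Protocol screens all year (Section 2.3.1) and has follow-up visits (Section 3.1), so a rule on repeat serum or interim vaccination may sit there. Section 6 also refers to each person's most recent titer, so one year is the outer limit and not the typical age of the serum.
- *That susceptibility at exposure cannot be known.* The admission HAI/FRNT sample can show it in retrospect, and Section 9.3 plans to relate immunological measures to infection risk. The gap is that the sample does not inform selection.
- *That the 25% SAR presupposes fully susceptible Recipients.* Section 9.2 calls it only an expected rate, and Section 2.3 ties it to low air hygiene and up to 60 hours of exposure.
- *That the predecessor trial shows the danger.* Section 2.1 attributes its low attack rate largely to mild illness and low shedding, not to Recipient immunity. It shows that an attack rate can fall short, but says nothing about this cause.

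Two safeguards also count. Randomization balances newly immune people between Intervention and Control Recipients in expectation, so that comparison is not confounded. Section 8.1.2 allows a controls-only first event to check SAR and power; it may detect a low SAR but cannot prevent one.

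What survives is narrower. A titer that can predate vaccination or infection is used for selection, and nothing in this document says what to do when that has happened.

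**Conclusion.** The point holds as a conditional weakness in Recipient selection. Following this Protocol as written can admit people whose qualifying titer is out of date. If 10% to 40% had become immune and are counted as non-cases, corrected power falls from 84% to between 79% and 57% at 54 per group, and from 86% (stated as 84%) to between 81.5% and 60% at 63 per group. If a 10% share are all counted as cases instead, it is about 62% at 54 per group.

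These figures rest on an assumed immune share, all-or-nothing immunity, equal groups and an inferred power formula. They do not show that the trial is underpowered. They show that the power claim is sensitive to something the Protocol could control cheaply.

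**What to change.** 1. At the existing invitation call, ask whether the person has had an influenza vaccine or known influenza since the qualifying serum. If so, do not select on that serum unless a later low titer is already available from the Recipient Protocol. State this in Section 4.1, or cite the Recipient Protocol if it already has the rule. A new titer for the purpose should be optional, because it adds a draw and an assay at the collaborating laboratory.
2. Invite first those with current-season serum and no interim vaccination or influenza. Ask no one to forgo vaccination.
3. In Section 9.1.3, name the admission sample as the serological baseline and condition the seropositive outcome on it, for example by counting a titer of 40 or more at one month only when the admission titer was below 40.

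The cost is one question, one eligibility line and a sharper endpoint definition. The pool for each cohort becomes smaller, which looks tolerable because Section 6 plans to enroll enough potential "recipients that only a fraction are needed in any one season". Undiagnosed infections will still be missed; Section 3.1 itself notes that many people with influenza-like illness may never have its cause diagnosed.
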